7.3.5 Laboratory Tests

The following laboratory parameters will be determined at the time points specified in the flow charts of assessments on pages 14 and 16 and in Section 6.

7.3.5.1 Central Laboratory

The following laboratory tests will be done at the central laboratory:

- **FVIII:**C in the vials used for PK injections as well as in plasma using the CHR and OS assays
- **FVIII inhibitor activity** will be determined at each study visit before the injection of *Wilate* using the modified Bethesda assay (Nijmegen modification). Blood sampling for inhibitor testing should preferably be performed at the time of trough FVIII:C levels.

If inhibitor development is suspected between study visits (e.g., based on an unexplained need to increase the dose, lack of efficacy of IMP injections, or prolonged bleeding) (see also **Section 6.1.8**), additional FVIII inhibitor tests will be performed and documented.

In case of positive inhibitor results, inhibitor retesting using a second, separately drawn sample should be performed, preferably within 15 days of becoming aware of the positive result. If inhibitor development is confirmed by the second sample analyzed in the central laboratory, patients with low-titer inhibitors (<5 BU) may continue treatment with *Wilate*, while patients with high-titer inhibitors will be discontinued from the study.

- VWF:Ag and VWF:Ac will be measured at prespecified time points.
 - **VWF:Ac** will be measured by INNOVANCE® VWF Ac (Siemens Healthcare Diagnostics), which is a particle enhanced assay for the automated determination of VWF activity in human citrated plasma. The assay principle makes use of the binding of VWF to its receptor Glycoprotein Ib (GPIb). GPIb is the main VWF receptor on platelets. Polystyrene particles are coated with an antibody against GPIb. Recombinant GPIb (two gain-of-function mutations included) is added and binds to the antibody as well as to the VWF of the sample. Due to the gain-of-function mutations, VWF binding to GPIb does not require ristocetin. This VWF binding induces a particle agglutination which can be measured as an increase in extinction by turbidimetric measurements.
- **Virus safety** will be evaluated by taking a plasma sample for parvovirus B19 antibody testing during the Screening Visit. All patients negative during screening will be tested again at the Study Completion Visit.
 - A retention serum sample for possible virus marker testing will be taken during the Screening Visit and stored at the central laboratory.

Central laboratory:

7.3.5.2 Local Laboratory

The following laboratory tests will be done by the local laboratories of each study site:

- **Hematology:** red blood cell count, white blood cell count, hemoglobin, hematocrit, and platelet count
- Chemistry: total bilirubin, alanine amino transferase, aspartate transaminase, blood urea nitrogen, serum creatinine

CD4+ and **AB0 blood-type testing** as well as **FVIII:**C **measurements in case of surgery** will also be done by the local laboratories. Samples for surgery-related FVIII:C testing will also be shipped to the central laboratory for OS and CHR assay assessments.

The methods of determination and normal ranges for each parameter will be provided in the clinical study report.

7.3.6 Vital Signs and Physical Examination

The vital signs obtained at the time points specified in **Section 6** are blood pressure, body temperature, heart rate, and respiratory rate.

Physical examinations will be performed at the visits specified in **Section 6**. Both height and weight will be measured at baseline. In addition, weight will be measured at all visits prior to dosing.

7.3.7 Other Relevant Safety Information

(a) Post-study related safety reports

After the Study Completion Visit, any thromboembolic events will continue to be monitored proactively by performing a Follow-up Contact 30 days after the Study Completion Visit (see **Sections 6.1.7** and **7.3.4**). They should be documented on AE page in eCRF.

In addition, any SAE which occurs up to 4 weeks after the last IMP administration should be reported by the Investigator to the Sponsor in case the Investigator becomes aware of it. Proactive monitoring for post-study SAEs is not required.

If any such post-study event is identified, the Investigator will complete an SAE form and transmit it to the Clinical Trial Manager (see **Section 7.3.4**).

Deaths occurring within 4 weeks after the last IMP administration should also be reported, regardless of whether or not they are considered treatment-related.

Overdose, interaction, medication error

The following safety relevant information should be reported as AE or, if the reaction fulfils one of the criteria for seriousness, as SAE.

(b) Drug overdose

An overdose is a deliberate or inadvertent administration of a treatment at a dose higher than specified in the protocol and higher than the known therapeutic dose that is of clinical relevance. The reaction must be clearly identified as an overdose.

(c) Drug interaction

A drug interaction is a situation in which a substance or medicinal product affects the activity of an IMP, i.e., increases or decreases its effects, or produces an effect that none of the products would exhibit on its own. The reaction must be clearly identified as a drug interaction.

(d) Medication error

A medication error involves the inadvertent administration or unintended use of a medicinal product which may be caused by the naming, presentation of pharmaceutical form/packaging, or instructions for use/labelling. The reaction must be clearly identified as a medication error.

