- [4] Before injection as well as 15±5 min after injection
- [5] Blood sampling within 1 h before injection and 15±5 min, 1 h (±5 min), 6 h (±30 min), 24±2 h, and 48±2 h after the end of injection [central laboratory]
- [6] Blood sampling within 1 h before injection as well as 15±5 min after the end of injection [central laboratory]
- [7] If first sample was negative for parvovirus B19 antibodies (sample to be taken before injection) [central laboratory]
- [8] CD4+ count to be repeated if interval between Screening Visit and first injection exceeds 30 days. To be included into the study, the patient's CD4+ count must be >200/μL (i.e., inclusion criterion no. 4).
- [9] Unless obtainable from patient's medical history
- [10] Blood sampling for inhibitor testing should preferably be done at the time of trough FVIII:C levels [central laboratory]

 In case of positive inhibitor results, inhibitor retesting using a second, separately drawn sample should be performed, preferably within 15 days of becoming aware of the positive result.
- [11] Documentation of any thromboembolic events only (to be documented on AE page)

FLOW CHART OF ASSESSMENTS FOR SURGICAL PROPHYLAXIS

	For details	Within	Within	Surgery		POP	Any POP day	End of POP period	3-8 weeks after surgery
	For details, see Section 12 hours before start		3 hours before start	Intra- operatively	End [1]	day 1			
Body weight		х							
Type of surgery		х							 
Location of surgery		х							 
Severity of surgery	7.2.5	х							
Expected duration of surgery		х							
Expected average/ maximum blood loss during surgery	7.2.5	х							 
Actual duration of surgery					Х				
Actual blood loss during surgery					Х				
Administration of IMP			х	(x)	(x)	(x)	(x)	(x)	
FVIII plasma levels	7.2.5		#	(#)	(#)	(#) [2]	(#)	(#)	 
VWF:Ag and VWF:Ac	7.3.5		#			(#) [2]	(#)	(#)	 
Presence of wound hematomas						Х	х	Х	I
Routine safety laboratory	7.3.5	х				(x)	(x)	(x)	
Vital signs	7.3.6	х		х		Х			
Efficacy assessment	7.2.6				S			Н	
Overall efficacy assessment	7.2.6								
Factor VIII inhibitor [3]	7.3.5								X
Narrative of outcome								Х	
Concomitant medications		throughout observation period							
Adverse event monitoring	7.3	throughout observation period							

POP = postoperative, VWF:Ag = von Willebrand factor antigen, VWF:Ac = VWF activity

- () Optional
- # Samples to be taken immediately before (≤ 30 min) and 30±15 min after IMP administration

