6.1 Observations by Visit for PK Assessment and Prophylactic Treatment

All enrolled patients will participate in the following study visits:

- Screening Visit
- PK Visit
- Day-14 Visit
- Day-30 Visit
- 3-Month Visit
- Completion Visit
- Follow-up Contact 30 days after Completion Visit

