6.1.7 Follow-up Contact 30 days after Study Completion Visit

The purpose of the Follow-up Contact 30 (\pm 3) days after the 6-month Study Completion Visit is to **document any thromboembolic events**, whether or not they are suspected to be related to study treatment.

The Follow-up Contact may take either the form of a personal visit by the patient to the study site or a telephone call by the Investigator. Any relevant AEs are to be recorded on the AE page of the eCRF.

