7.3.2.2 Collection of AEs

The condition of the patient will be monitored throughout the study. At each visit, whether scheduled or unscheduled, AEs will be elicited using a standard nonleading question such as "How have you been since the last visit/during the previous study period?" In addition, the Investigator will check the patient diaries for any documented event.

Any AE or ADR which occurs during the study will be noted in detail on the appropriate pages of the CRF. If the patient reports several signs or symptoms representing a single syndrome or diagnosis, the diagnosis should be recorded in the CRF. The Investigator will grade the severity of all AEs or ADRs (mild, moderate, or severe), the seriousness (non-serious or serious), and the causality as defined in **Sections 7.3.2.3**, **7.3.3**, and **7.3.2.4**. The Sponsor is responsible for assessing the expectedness of each ADR (expected or unexpected) as defined in **Section 7.3.2.5**.

In the event of clinically significant abnormal laboratory findings, the tests will be confirmed and the patient followed up until the laboratory values have returned to normal and/or an adequate explanation for the abnormality has become available.

Diseases, signs and symptoms, and/or laboratory abnormalities already present before the first administration of IMP will not be considered AEs unless an exacerbation in intensity or frequency (worsening) occurs.

The Investigator will provide detailed information about any abnormalities and about the nature of and reasons for any action taken as well as any other observations or comments that may be useful for the interpretation and understanding of an AE or ADR.

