2.4 Study design

This study is designed as a prospective, non-controlled, international, multi-center phase 3 study. Further details are given in the overview below:

FLOW CHART FOR PK ASSESSMENT AND PROPHYLACTIC TREATMENT

| | Screening Visit | PK Visit | Prophylactic Treatment Phase (starts with first prophylactic injection of Wilate after the PK Visit) | | | | Follow-up Contact 30 (±3) days after Study Completion Visit |
|---|-----------------|----------|--|------------------------|--------------------------|---|---|
| | | | Day-14 Visit (14–21 days) | Day-30 Visit (±3 days) | 3-Month Visit (±2 weeks) | Study Completion (6-Month) Visit at 6 months (+2 weeks) | |
| Informed consent | x | | | | | | |
| Inclusion and exclusion criteria | x | | | | | | |
| Demographics | x | | | | | | |
| Weight | x | x [1] | | | x [1] | x [1] | |
| Height | x | | | | | | |
| Medical history (incl. FVIII treatment 6 months before screening) | x | | | | | | |
| Vital signs | x | x [2] | | | x [4] | x [4] | |
| Physical examination | x | | | | | x | |
| Routine safety laboratory | x | x [3] | | | x [1] | x [4] | |
| Determination of CD4+ levels [8] | x | | | | | | |
| Determination of AB0 blood group [9] | x | | | | | | |
| HJHS, unless obtained within 3 months before screening | x | | | | | | |
| PK injection (50 ± 5 IU/kg) | | x | | | | | |
| Blood sampling for FVIII:C (OS and CHR) for PK assessment | | x [5] | | | | | |
| IVR injection | | | | | x | x | |
| Blood sampling for FVIII:C IVR (OS and CHR) | | | | | x [6] | x [6] | |
| Factor VIII inhibitor [10] | x | x [1] | x [1] | x [1] | x [1] | x [1] | |
| VWF:Ag and VWF:Ac | | x [6] | x [1] | x [1] | x [6] | x [6] | |
| Parvovirus B19 antibodies | | x [1] | | | | x [7] | |
| Retention sample for possible virus marker testing | | x [1] | | | | | |
| Patient diary review | | | x | x | x | x | |
| Adverse event monitoring | | x | » | » | » | x | x [11] |
| Concomitant medications | x | » | » | » | » | x | |

PK = pharmacokinetic, IVR = in vivo recovery, HJHS = Hemophilia Joint Health Score, OS = one-stage assay, CHR = chromogenic assay, VWF:Ag = von Willebrand factor antigen, VWF:Ac = VWF activity

STATISTICAL ANALYSIS PLAN

Protocol No: WIL-30

Version Number: 1.2

Date of Issue: 2019-07-08

Page 12 of 27

LEGEND TO THE FLOW CHART FOR PK ASSESSMENT AND PROPHYLACTIC TREATMENT

- [1] Before injection
- [2] Before injection as well as 1 h (± 5 min) and 48 ± 2 h after injection

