5.10.1 Adverse events

Adverse events (AEs) will be coded by the CRO according to the latest Medical Dictionary for Regulatory Activities (MedDRA). Coding will be agreed upon with the Sponsor before database lock (cf. DMP).

All adverse events recorded since signing of the informed consent form (ICF) will be listed in appendix 16.2 of the report differentiating by treatment emergent and non-treatment emergent events. This includes also post-study serious adverse events (SAEs) which occurred up to 4

| | |
|--|---------------|
| 
STATISTICAL ANALYSIS PLAN Protocol No: WIL-30
 | |
| Version Number: 1.2 | Page 22 of 27 |
| Date of Issue: 2019-07-08 | |

weeks after the last IMP administration (not monitored proactively), thromboembolic events monitored proactively by performing a Follow-up Contact 30 days after the completion visit as well as safety relevant information on drug overdosing, drug interactions and medication errors.

The analysis will include only treatment-emergent adverse events (TEAEs), i.e. all documented AEs that started or worsened after the start of IMP infusion. It is assumed that for each increase in intensity of an AE a new entry of the AE will be done by the investigator; hence such cases will be analyzed like different phases of the same AE.

A descriptive analysis will be performed. Incidences will be presented by primary system organ classes (SOC) and incidences of PT within primary SOC sorted according to the Internationally Agreed Order.

Multiple counts within a PT or SOC (repeated or different included terms or changes in descriptors) will be counted only once for the calculation of incidences.

Global incidences will be calculated for:

- All TEAE irrespective of the causality assessment
- Related TEAEs ('Probably' or 'Possible')
- TEAEs by worst severity
- Serious TEAEs

A listing of "special cases" containing subject identification, age, sex, AE descriptors, start and end of treatment will be prepared for the following types of TEAEs:

- Serious adverse events (SAE)
- Adverse events which led to death
- Adverse events which led to discontinuation

Serious non-treatment emergent AEs will be listed separately.

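### The 30-day contact made for every child covers thromboembolic events only, so other post-study SAEs are captured passively yet count in the serious-TEAE tables

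*Protocol*

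**What the plan says.** **Who is contacted, and when.** Protocol 6.1 states that "All enrolled patients will participate in the following study visits" and puts the follow-up contact last in the list. The flow chart in SAP 2.4 heads the column "Follow-up Contact 30 (±3) days after Study Completion Visit".

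**What is asked.** Protocol 6.1.7 gives the purpose as to "document any thromboembolic events". Footnote [11] is stricter, and reads the same in the Protocol and SAP legends: "Documentation of any thromboembolic events only (to be documented on AE page".

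**Other SAEs.** Protocol 7.3.7(a) has SAEs within four weeks of the last dose reported if the investigator comes to know of them, and then says "Proactive monitoring for post-study SAEs is not required". Deaths in that period have their own sentence in 7.3.7 and a note in 7.3.2.6. Neither depends on the investigator happening to learn of the death.

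**How they are used.** Protocol 7.3.1 includes post-study SAEs in the safety information to be collected. SAP 5.10.1 (version 1.2) puts them in the adverse-event listing and labels them: up to 4 "weeks after the last IMP administration (not monitored proactively"). Protocol 7.3.2.1 and 9.2.3 and SAP 5.10.1 define a TEAE by its onset or worsening after the start of infusion and set no end to the period. Serious TEAEs are tabulated.

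**Two wider sentences.** Protocol 6.1.7 also says "Any relevant AEs are to be recorded on the AE page of the eCRF", without saying what makes an event relevant. Protocol 7.3.2.2 says "At each visit, whether scheduled or unscheduled, AEs will be elicited using a standard nonleading question", without saying whether a telephone contact counts as a visit.

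**The concern.** The plan contacts every family at almost exactly the time when the four-week SAE window closes, but does not ask about SAEs other than thromboembolic ones. Whether another serious event enters the database then depends on whether someone tells the site.

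Two things are at stake. First, the serious-TEAE table would combine an actively monitored treatment period with a passively monitored tail, because nothing in the TEAE definition cuts the tail off. Second, sites may act differently. With about 5 sites and 10 children, a site that takes the sentence on relevant events broadly and a site that follows the footnote literally could produce different safety records from the same events.

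The interval also has some importance of its own. Protocol 7.3.3 makes inhibitor development and suspected transmission of an infectious agent SAEs. Under 6.1.6 the final inhibitor and parvovirus samples are drawn before the last injection. No scheduled test follows that dose, apart from a post-surgery inhibitor test where one falls due (7.2.5). The contact is therefore the scheduled occasion for hearing of such a diagnosis made elsewhere.

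**Working it through.** The documents give no figure on this point, so there is nothing to reproduce. The check compares the two windows, sizes the passive one, and illustrates what passive capture could cost.

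**1. Do the windows coincide?** For completers the last prophylactic dose is given at the Study Completion Visit (Protocol 6.1.6). Call that day 0.
- SAE window (7.3.7): day 0 to 4 × 7 = 28.
- Contact: 30 − 3 = day 27 to 30 + 3 = day 33.

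A contact on day 28 to 33 covers the whole window. The earliest permitted contact misses 28 − 27 = 1 day. A child who withdraws early may have had the last dose before the Study Completion Visit, so the windows need not line up.

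**2. How large is the passive window?** Inputs: 10 children enrolled (Protocol 4.1.1) and 6 months of prophylaxis (5.4.2).
- Passive window: 10 × 28/365.25 = 0.77 patient-years.
- On treatment: 10 × 0.5 = about 5 patient-years.
- Ratio: 0.77/5 = about 15%.

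As a share of one child's observation from first dose (2 PK days + 182.6 days + 28 days), it is 28/212.6 = 13.2%. With the extra two weeks allowed at completion it is 28/226.6 = 12.4%.

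**3. What could passive capture cost?** Neither the four-week SAE risk p nor the probability c that a passive system records an SAE is in the documents. Both are assumptions here. The chance that at least one post-study SAE is recorded among 10 children is 1 − (1 − p·c)^10:

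| Assumed p | All asked (c = 1) | c = 0.8 | c = 0.5 | c = 0.3 |
|---|---|---|---|---|
| 2% | 18.3% | 14.9% | 9.6% | 5.8% |
| 5% | 40.1% | 33.5% | 22.4% | 14.0% |
| 10% | 65.1% | 56.6% | 40.1% | 26.3% |

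**4. What does a zero count mean?** The exact two-sided 95% upper limit for 0 of n is 1 − 0.025^(1/n).
- n = 10, all asked: 30.8%. For n = 8 it is 36.9%.
- n = 10, passive: the limit applies to p·c, so for p it is 0.3085/c. This gives 38.6% at c = 0.8 and 61.7% at c = 0.5. At c = 0.3 the quotient exceeds 1, so a zero says nothing about p.

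**5. Do the wider sentences close the gap?** No. The sentence on relevant events in 6.1.7 says where to record an event and does not require anyone to ask. The visit question in 7.3.2.2 is general, whereas the footnote restricts this particular contact and 7.3.7 expressly waives active follow-up of SAEs. The specific provisions govern, but the wording still has to be reconciled.

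**The case against.** The strongest reply is that this is a deliberate, disclosed choice in a small descriptive PK study. Several parts of that reply stand.

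- **Deaths.** A reader might infer that deaths, too, are reported only if the site happens to hear of them. The text does not support that: the condition is attached to SAEs, and the provisions on deaths are unconditional, although no active inquiry is set out.
- **Disclosure.** A reader might infer that the SAP hides the mixing of active and passive data. It does not. The sentence that lists post-study SAEs marks them as passively obtained and marks thromboembolic events as actively monitored. No separate post-study SAE rate is planned.
- **Chance capture.** A reader might say that SAEs surface only by luck. That is too strong. The investigator speaks to or sees every family, and an SAE mentioned then makes the investigator aware and brings in the SAE form. Passive is the exact word.
- **Inhibitors and infection.** A question cannot detect either. Inhibitors are found by assay, and 7.3.3 ties suspected virus transmission to detected antigen. The question helps only if the child has already been tested.
- **Little information either way.** With all 10 children asked, zero events still leaves an upper limit of 30.8%.
- **Versions.** The protocol supplied is Version 02, for Ukraine only. SAP 1.2 also cites a Version 03 that was not available, so whether 7.3.7 stood unchanged there cannot be confirmed.

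None of this removes the core. The contact exists, its timing fits, its content is restricted, and any events reported afterwards count as TEAEs.

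**Conclusion.** The point holds as a minor weakness in data capture. Non-thromboembolic SAEs in the four weeks after the last dose are obtained passively, over about 0.77 patient-years (roughly 15% on top of about 5), and any that are reported join the actively collected events in the serious-TEAE incidence. It is not a hidden contradiction, and no endpoint derivation is shown to be wrong.

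The size assumes that all 10 children complete about six months and take the last dose at the Study Completion Visit. It measures exposure without active inquiry and says nothing about how many SAEs are missed. The capture illustrations depend wholly on the assumed p and c. The conclusion rests on the protocol version supplied.

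**What to change.** **For data still to be collected**
- Protocol 6.1.7 and footnote [11] in both legends: have the existing contact, made no earlier than 28 days after the last dose, ask about any SAE since that dose as well as thromboembolic events. Counting from the last dose also deals with early withdrawers who are contacted.
- Reconcile the sentence on relevant adverse events in 6.1.7 with the restriction in footnote [11], so that all sites ask the same thing.
- Protocol 7.3.7(a): for the four-week window, remove both the clause that makes SAE reporting depend on the investigator's becoming aware and the sentence "Proactive monitoring for post-study SAEs is not required". Removing only the second would leave 7.3.7 at odds with the amended 6.1.7.
- SAP 5.10.1: change the passive label only for data collected under the amended rule.

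**For data already collected.** SAP 1.2 was issued after the Database Review Meeting, so collection may be over. In that case keep the label, which is accurate, and state in the study report that post-study SAE capture was passive and that a zero count does not show absence.

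**Cost.** One more question in a contact that already takes place, and a few more SAE forms. No new visit or sample is needed.
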